12.6 Data Analysis Plans

The primary analysis will compare the observed OR and CR rates to posited null values of 30% and 10%, respectively. We will calculate score-based confidence intervals for binomial proportions. At the critical values of 17/33 and 7/33, the confidence intervals for the ORR and CRR would be (35.2%, 67.5%) and (10.7%, 37.8%), respectively. The analyses of secondary safety objectives will be conducted using tabulations of adverse events, stratified by grade and attribution.

The analyses corresponding to secondary efficacy endpoints (PFS, DCR, DOR, TNT) will be summarized with typical ‘time-to-event’ analyses.

With regard to the exploratory objectives, we will evaluate pre-post changes in LAM, Treg, CTL, “exhausted” T cell, and MDSC densities, as well as lymphoma cell and tumor microenvironment expression of PD-L1 and CSF-1R. We posit that changes in some or all of these biomarkers will correlate with response, thus demonstrating potential as prognostic biomarkers. We will also evaluate MRD status in patients achieving CR and hypothesize that patients with CR but detectable MRD will predict relaps. We will quantify these associations using visual and statistical summarization.

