1.6.2.1 Phase 1a Dose Escalation (Monotherapy)

Adverse Events

As of 02-Jul-2018, AEs were experienced by 22 of 24 (91.7%) subjects treated in Phase 1a monotherapy dose-escalation cohorts. There were no Grade 5 AEs experienced by any subject in Phase 1a monotherapy dose-escalation cohorts.

Treatment-related AEs

Treatment-related AEs were experienced by 17 of 24 (70.8%) subjects who received cabiralizumab monotherapy. The most commonly reported ($\geq 25\%$ of subjects) treatment-related AEs included AST increased (8 [33.3%] subjects), fatigue and periorbital oedema (7 [29.2%] subjects each), and blood creatine phosphokinase increased (6 [25.0%] subjects). The incidence of the treatment-related AEs that occurred in $> 10\%$ of the subjects is listed in Table 5.5.3.1-1 located in cabiralizumab IB v6. There were no Grade 5 treatment-related AEs experienced by any subject in Phase 1a monotherapy.

Serious Adverse Events

Of the 24 subjects receiving cabiralizumab monotherapy, 8 (33.3%) subjects experienced at least 1 SAE. Treatment-related SAEs occurred in 2 of 24 (8.3%) subjects and included Grade 3 blood creatine phosphokinase increase (1 [4.2%] subject) and Grade 3 rash (1 [4.2%] subject).

Dose-limiting Toxicities

Four DLTs were reported in the Phase 1a monotherapy arms of this study. One of the DLTs was a Grade 3 CK increase, and the other 3 DLTs were Grade 3 AST increases. The Grade 3 CK increase and 1 Grade 3 AST increase occurred at 6 mg/kg cabiralizumab monotherapy, and the other 2 Grade 3 AST increases occurred at 4 mg/kg cabiralizumab monotherapy. All DLTs resolved after discontinuation of study drug with no sequelae. These DLTs were all attributed to isolated increases in laboratory values (3 subjects due to elevation of AST and 1 subject due to elevation of CK), which were expected with administration of FPA008 due to diminished clearance of ALT, AST, CK, and LDH molecules from serum secondary to a reduced number of liver Kupffer cells. Based on this information, the management algorithms for hepatic AEs and liver enzyme alterations have been subsequently amended to allow higher cutoffs for these laboratory values as described in sections 17.1.2 and 17.1.3.

Discontinuations

A total of 3 of 24 (12.5%) subjects receiving cabiralizumab monotherapy discontinued study treatment due to a treatment-related AE, including Grade 3 AST increased (2 [8.3%] subjects) and Grade 3 blood creatine phosphokinase increased (1 [4.2%] subject).

Deaths

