1.6.3 Clinical Experience Involving Serum Enzyme Elevations

The safety and preliminary efficacy of cabiralizumab has been evaluated in multiple clinical trials as described in IB v6. A common feature observed across the clinical trials is an elevation of AST, CK, and LDH after the administration of cabiralizumab. These alterations are the consequence of the direct effect of anti-CSF1R antibodies on the Kupffer cell in the liver that results in a depletion of these cells. Depletion of Kupffer cells allows the enzymes, which are released following normally occurring liver cell turnover, to enter circulation (where they are measured by routine laboratory assessment) rather than being absorbed by the Kupffer cells. Elevated liver enzymes, thus, represent a PD marker rather than a safety signal. The observed elevations were asymptomatic not permanent and not associated with clinical sequelae. Similar effects have been observed across other CSF1R targeted agents (see cabiralizumab IB for additional details). The data with cabiralizumab and with other agents in the class suggest that the observed serum enzyme elevations do not compromise the safety profile of cabiralizumab and therefore support modification of the safety monitoring criteria.

Serum Enzyme Elevations in Cabiralizumab

See above sections for descriptions of serum enzyme elevations in various clinical trials. Based on phase 1a data from FPA008 003, the management algorithms for hepatic AEs and liver enzyme alterations have been subsequently amended to allow higher cutoffs for serum hepatic enzyme elevations as described in sections 17.1.2 and 17.1.3.

The new algorithms have been used to re-evaluate the safety of 4 mg/kg cabiralizumab monotherapy (7 subjects) and 4 mg/kg cabiralizumab in combination with 3 mg/kg nivolumab (3 subjects). No DLTs were reported in subjects treated at these doses under the revised algorithms.

Since then, approximately 274 subjects have been treated with 4 mg/kg cabiralizumab in combination with 3 mg/kg nivolumab using the new management algorithms for hepatic AE and liver enzyme, and no Grade 5 hepatic events have been reported, thus confirming the validity of the management algorithms.

Management of Isolated Laboratory Abnormalities

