7. STUDY CALENDAR & EVALUATIONS

	Screen	Cycle Number ²					6 months post CR ¹⁰ / observation	Safety follow up 30 days ^{2,3} post last dose	Long-term Follow up ⁴ Every 3 months (±14 days)
	-28 days	1	2	3	4	5+			
		D1 ¹	D1	D1	D1	D1			
Cycle= 14 days									
REQUIRED ASSESSMENTS									
Review of eligibility criteria, Informed Consent	X								
Medical History ¹⁶ , Diagnosis and Staging (Lugano ⁵)	X								
Physical Exam, Vital Signs ⁶ , ECOG PS ⁷	X	X	X	X	X	X ¹⁷	Q3 mos	X	
EKG	X								
AEs & Concomitant Medications	X	X	X	X	X	X		D30, 100 ³	X ³
LABORATORY ASSESSMENTS									
Complete blood cell count with differential (CBC) ¹⁵	X	X	X	X	X	X	Q3 mos	X	
Comprehensive metabolic profile (CMP) ^{8, 15}	X	X	X	X	X	X	Q3 mos	X	
Mineral panel (phosphorus, magnesium, calcium) ¹⁵	X	X	X	X	X	X	Q3 mos	X	
Creatine kinase, LDH ¹⁵	X	X	X	X	X	X	Q3 mos	X	
Amylase, lipase ¹⁵	X	X	X	X	X	X	Q3 mos	X	
TSH, free T4, cortisol ¹⁵	X	X		X		C5, 7, etc	Q3 mos	X	
Pregnancy test (serum or urine) in WOCBP ⁹	X	X		X		C5, 7, etc ⁹			
DISEASE ASSESSMENT									
PET/CT Scan ¹⁰	-30d					X ¹⁰	Q6 mos		
Bone marrow aspirate and biopsy (unilateral) ¹¹	X					X	X ¹¹		
TREATMENT EXPOSURE									
Nivolumab 240 mg IV		X	X	X	X	X			
Cabiralizumab 4 mg/kg IV		X	X	X	X	X			
CORRELATIVE STUDIES (SPECIMEN COLLECTION)									
Fresh tumor tissue biopsy ¹²	X					C5 ¹³ , @PR ¹³			
Whole blood for somatic baseline		X							
PBMCs and plasma ¹⁴		X		X		C5,@imaging	@imaging	X	
BANKING SAMPLES (SPECIMEN COLLECTION)									
Whole Blood ¹⁴		X		X		C5, @imaging	@imaging	X	
Serum		X		X		C5, @imaging	@imaging	X	
Tumor Tissue ¹²	X					C5 ¹³ , @PR ¹³			
FOLLOW-UP									
Disease progression									X

Key to Footnotes

¹If screening (baseline) labs were performed within 7 days of C1D1 of treatment, these do not need to be repeated.

²A window of 3 days will be applied to all treatment study visits; for safety follow-up visit, tumor imaging, bone marrow biopsy, and lymph node biopsy, a 7-day window will apply.

³A safety follow-up visit will occur 30 days (± 7 days) after the last dose of treatment. Subjects who have an ongoing \geq grade 2 or serious AE (SAE) at this visit will continue to be followed until the AE resolves to \leq Grade 1 or baseline, is deemed clinically insignificant, and/or until a new anti-cancer treatment starts, whichever is earlier. AEs will be collected for 100 days (± 14 days) after the end of treatment. See Section 11.2.

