11. ADVERSE EVENTS

11.1 Definitions

11.1.1 Adverse Event (AE)

An AE is any untoward medical occurrence whether or not considered related to the study drug that appears to change in intensity during the course of the study. The following are examples of AEs:

- Unintended or unfavorable sign or symptom
- A disease temporally associated with participation in the protocol
- An intercurrent illness or injury that impairs the well-being of the subject

Abnormal laboratory values or diagnostic test results constitute AEs only if they induce clinical signs or symptoms or require treatment or further diagnostic tests

Hospitalization for elective surgery or routine clinical procedures that are not the result of an AE (e.g., surgical insertion of central line) should not be recorded as an AE.

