11.2 Reporting

11.2.1 Adverse Events

- AEs will be recorded from time of signed informed consent until 100 days after discontinuation of study drug(s).
- AEs will be recorded regardless of whether or not they are considered related to the study drug(s).
- All AEs will be recorded in the subject's medical record and on the appropriate study specific eCRF form within the EDC system.
- All AEs considered related to study drug(s) will be followed until resolution to \leq Grade 1 or baseline, deemed clinically insignificant, and/or until a new anti-cancer treatment starts, whichever occurs first.
- Asymptomatic laboratory abnormalities that do not require treatment will not be collected as adverse events.

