Safety assessments will consist of the surveillance and recording of AEs and documentation of physical examination findings and laboratory data. Type, incidence, severity, seriousness, and relatedness of adverse events will be recorded. Additional secondary analyses include PFS, DCR, DOR, and TNT.

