17.2 Laboratory abnormalities management

Laboratory Abnormalities Management (CK and LDH)		
Grade of Liver Test Elevation	Management	Follow-Up
CK > 10 xULN	
 - Measure CK isoenzymes - Obtain EKG to evaluate arrhythmia/myocarditis 	
If CK isoenzymes are abnormal
 
 - Check troponin levels - Consider other assessments (including uromyoglobin and echocardiogram) as clinically indicated 
If CK isoenzymes are normal
 
 - Continue dosing, per protocol - Monitor CK level as clinically indicated
CK or LDH > 15 to ≤ 20 xULN	
 - Delay cabiralizumab therapy per protocol^a - Measure CK isoenzyme panel to identify source of elevation, if abnormal check troponin and consider other assessments as clinically indicated - Increase frequency of monitoring (every 48-72 hours, or more, as clinically indicated) - Obtain EKG to evaluate arrhythmia/myocarditis - Notify the Sponsor Investigator 	
If returns to ≤ 15 xULN within ≤ 28 days:
 
 - Resume routine monitoring, resume cabiralizumab and nivolumab therapy at same dose level per protocol - If CK isoenzyme panel is normal continue monitoring the subject. - If CK isoenzyme panel is abnormal then consider measuring troponins. - If troponins are abnormal, contact Sponsor Investigator to determine if the subject can be retreated. 
If elevations persist at the same level > 28 days or worsen:
 
 - Discontinue further dosing - Discuss with Sponsor Investigator
CK or LDH > 20 xULN	
 - Discontinue cabiralizumab therapy per protocol - Obtain EKG to evaluate arrhythmia/myocarditis 	
 - Follow up until resolution

- a. If the AE requiring dose delay was due to one of the study drugs, the non-offending drug may be continued, taking into account the safety and clinical benefit to the patient.
- b. If the AE requiring discontinuation was due to one of the study drugs, the non-offending drug may be continued, if there is timely resolution of AE and clinical benefit is shown by patient

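### The end-of-study safety analysis uses adverse events only, while 11.1.1 and 11.2.1 disagree on which laboratory abnormalities become adverse events

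*Combined protocol and SAP*

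**What the plan says.** Safety and tolerability of the combination is a secondary objective (2.1.2). For its analysis, 12.6 states: "The analyses of secondary safety objectives will be conducted using tabulations of adverse events, stratified by grade and attribution". Section 12.6.2 refers back to 12.3, which says: "Safety assessments will consist of the surveillance and recording of AEs and documentation of physical examination findings and laboratory data". That provides for laboratory data to be recorded but not summarised, and 12.6.4 plans nothing further. Section 12.3 also sets three interim AE thresholds on the first 17 patients, two of them counts of patients with Grade 4 AEs.

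Two sections decide which laboratory abnormalities become AEs. The definition in 11.1.1 reads: "Abnormal laboratory values or diagnostic test results constitute AEs only if they induce clinical signs or symptoms or require treatment or further diagnostic tests". The collection rule in 11.2.1 reads: "Asymptomatic laboratory abnormalities that do not require treatment will not be collected as adverse events".

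The study calendar schedules blood counts, the metabolic panel (with AST, ALT and bilirubin), amylase and lipase on day 1 of every cycle, together with the row "Creatine kinase, LDH ¹⁵". On the drug itself, 1.6.3 says: "A common feature observed across the clinical trials is an elevation of AST, CK, and LDH after the administration of cabiralizumab". The same section describes these elevations as asymptomatic. Of the Phase 1a monotherapy dose-limiting toxicities, 1.6.2.1 says: "These DLTs were all attributed to isolated increases in laboratory values". Section 10.1.6 lists raised CK, LDH, AST and ALT among the most common events with cabiralizumab.

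**The concern.** The laboratory effects expected most often from cabiralizumab are, by the protocol's account, mostly silent. An analysis built only on AE records, with a collection rule that turns away silent and untreated abnormalities, will understate them even though the values are measured every two weeks.

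These values also drive dosing. In 17.2, CK or LDH above 20 xULN carries the instruction "Discontinue cabiralizumab therapy per protocol", with an EKG but no treatment listed. Under the 11.2.1 wording, such a patient could stop cabiralizumab with no matching AE row; under 11.1.1 the same patient has one. Sites could resolve this differently, so AE rates could depend partly on which section a site follows. The interim Grade 4 counts use the same AE records.

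**Working it through.** **Step 1. Asymptomatic, untreated findings set against both sections.** Thresholds and actions come from 17.1.2, 17.1.3, 17.2, 6.3 and 11.1.6.

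| Finding | Listed action | AE under 11.1.1 | Collected under 11.2.1 |
|---|---|---|---|
| AST/ALT up to 5 xULN, bilirubin and INR below their triggers | none | no | no |
| CK up to 10 xULN | none in 17.2 | no | no |
| LDH up to 15 xULN | none | no | no |
| AST/ALT >5 to 12 xULN | dosing continues; liver tests and INR every 48–72 h | yes, if added monitoring counts as further tests | no |
| CK >10 to 15 xULN | isoenzymes, EKG | yes | no |
| AST/ALT >12 to 20 xULN, settling within 7 days | both drugs delayed; liver tests and INR every 48–72 h | yes, same proviso | only if steroids are given |
| AST/ALT >12 to 20 xULN, lasting over 7 days | steroids | yes | yes |
| AST/ALT >20 xULN | both drugs stopped; tests every 1–2 days; steroids to be considered | yes, same proviso | only if treated |
| CK or LDH >15 to 20 xULN | cabiralizumab delayed; isoenzymes, EKG | yes | no |
| CK or LDH >20 xULN | cabiralizumab stopped; EKG | yes | no |
| Isolated Grade 4 amylase or lipase | medical monitor consulted (6.3); no test or treatment named | not clearly | no |
| Potential DILI | reported as SAE | yes | yes, as SAE |

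The first three rows are outside the AE data under both sections, unless an investigator orders tests or treatment. One qualification applies to CK: 1.6.3 and 6.3 mention CK subsets and troponin whenever CK is elevated, but 6.3 defers to 17.2, where the first threshold is 10 xULN. On the broader reading, lower CK rises move into the conflict group. In the middle rows the sections disagree. Steroid-treated and potential-DILI cases are collected either way.

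**Step 2. How common such events were (1.6.2.1, monotherapy).** AST increased 8/24 = 33.3%; CK increased 6/24 = 25.0%; treatment-related discontinuation 3/24 = 12.5% (two AST, one CK, so all were enzyme rises). These match the stated percentages. They are events that were reported as AEs, so they carry no information on the share that would go unreported here.

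**Step 3. The interim rule that depends on AE capture.** Let X ~ Binomial(17, p) be the number of patients with a Grade 4 AE; enrolment stops if X ≥ 7.

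- At p = 0.50, P(X ≥ 7) = 0.834. This reproduces the 12.3 statement that the trial stops with probability at least 0.83.
- At p = 0.32, P(X ≥ 7) = 0.284. At the null (CRR 10%, ORR 30%) the exact futility-stop probability is 0.649. Treating toxicity as independent, the combined stop is 1 − (1 − 0.649)(1 − 0.284) = 0.749, against about 0.75 in 12.3.

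Suppose a share s of patients with a Grade 4 event have only uncollected laboratory events of that grade. The counted rate is then p(1 − s). The documents do not give s; the values below are assumptions.

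| True rate p | s | Counted rate | P(X ≥ 7) |
|---|---|---|---|
| 0.50 | 0 | 0.50 | 0.834 |
| 0.50 | 10% | 0.45 | 0.710 |
| 0.50 | 25% | 0.375 | 0.467 |
| 0.50 | 50% | 0.25 | 0.107 |
| 0.32 | 0 | 0.32 | 0.284 |
| 0.32 | 25% | 0.24 | 0.089 |
| 0.32 | 50% | 0.16 | 0.012 |

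If the 32% and 50% in 12.3 are meant as rates of collected AEs, the printed operating characteristics stand. They then describe only the toxicity that is collected.

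**The case against.** A reader might infer that all the enzyme rises, including those that delay or stop dosing, would be absent from the safety results. The documents do not support that. Under 11.1.1 those cases are AEs because the management tables order further tests or closer monitoring. The protocol's own language agrees: the liver tables are headed as adverse event management, and the footnote on the CK/LDH delay row of 17.2 speaks of an AE. Persistent AST/ALT elevation above 12 xULN leads to steroids and so passes 11.2.1. Section 6 has subjects evaluated for AEs that interrupt or stop drug, 6.3 puts the reason for discontinuation on the eCRF, and 5.2 records each administration date there. This stands. It makes capture contradictory rather than absent, because 11.2.1 is the section that tells sites what to collect, and it does not repeat the further-tests criterion.

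A reader might also multiply the Phase 1a rates by 33 and take the result as the number of patients lost. That is unsound: those rates count reported events, under monotherapy, and the discontinuations preceded the higher enzyme cut-offs. Nor is 12.6 the only safety analysis, since 12.3 has the interim rules, although they draw on the same AE data.

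Finally, 1.6.3 regards the liver-enzyme elevations as a pharmacodynamic effect, not a safety finding. That is a fair clinical interpretation, but the protocol still delays or stops dosing on these values, and a pharmacodynamic effect also merits a summary. Laboratory data are documented, so nothing is irretrievable; what is missing is a planned analysis.

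**Conclusion.** The point holds in a limited form. The end-of-study safety analysis is AE tabulation alone, with no planned summary of laboratory values. Asymptomatic, untreated AST/ALT, CK and LDH rises below the action thresholds would be left out of the safety tables under either section. For rises that delay or stop dosing, 11.1.1 and 11.2.1 conflict, so capture is undetermined, and the Grade 4 counts in 12.3 share that uncertainty. Symptomatic, steroid-treated and potential-DILI cases are captured. Discontinuation reasons are recorded but not tabulated.

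The size of the loss cannot be derived from the documents. The Step 3 probabilities depend wholly on the assumed non-capture share and on applying it to the 7-of-17 rule alone. They show that the rule is sensitive to capture, not that it will fail. The appendices tie actions to multiples of ULN, and the documents do not reproduce the CTCAE grades for these enzymes, so how many of the affected values would be Grade 4 is also not established here. The change is worth making before analysis; it does not put the efficacy design in doubt.

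**What to change.** 1. Add to 12.6 a laboratory summary taken from measured values, independent of AE reporting. For AST, ALT, bilirubin, CK, LDH, amylase, lipase, ANC, hemoglobin and platelets, give each subject's worst post-baseline value and the shift from baseline. Use the protocol's own bands: AST/ALT above 5, 12 and 20 xULN; CK above 10, 15 and 20 xULN; LDH above 15 and 20 xULN. State that AE tabulations alone are not the basis for laboratory toxicity rates.
2. Add a table of dose delays and discontinuations by reason, with laboratory-triggered ones shown separately.
3. Reconcile 11.1.1 with 11.2.1 so that one rule applies at every site. State whether a laboratory abnormality that leads to delay or discontinuation is collected as an AE, and whether it counts in the 12.3 Grade 4 rules. Say whether the 32% and 50% rates in 12.3 are meant on that same basis.

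The cost is a paragraph in 12.6, one or two extra tables and a short edit to section 11, with no new visits or assays. Two practical checks follow. Section 14.2 lets some standard-of-care results stay in source documents, so confirm that these analytes and the local ULNs are in the EDC. The protocol names an eCRF entry for the reason for discontinuation but not for the reason for delay, so a field may be needed. The reported toxicity profile will probably look somewhat less favourable. No dosing or management rule changes.

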The median overall survival of relapsed/refractory PTCL in patients that are not candidates for high-dose therapy and autologous stem-cell transplantation is <6 months[12, 13]. The dismal outcomes observed in relapsed/refractory PTCL are explained, at least in part, by the high-rate of chemotherapy resistance and high proliferation rates observed. The aggressive behavior of these lymphomas poses a challenge for immunotherapeutic strategies, as disease progression may outpace the host anti-tumor immune response elicited by therapeutic strategies, including checkpoint blockade, leading to cytotoxic failure. Therefore, therapeutic strategies, including CSF-1R inhibition, that may bolster anti-tumor immunity (upon LAM depletion) and slow the rate of disease progression (due to inhibition of CSF-1R's cell-autonomous effects on malignant lymphocytes) are extremely attractive.

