9.3.4 Progression Free Survival

A measurement from the date of enrollment until the criteria for disease progression (PD) is met or death occurs. Subjects who have not progressed will be right-censored at the date of the last disease evaluation.

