9.3.5 Disease Control Rate

The disease control rate (DCR) is the proportion of all subjects with stable disease (SD) for 8 weeks, PR, or CR.

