9.3.6 Duration of Response

Duration of response is the period measured from the time that measurement criteria are met for CR or PR (whichever status is recorded first) until the date that recurrent or progressive disease is objectively documented (taking as reference for progressive disease the smallest measurements recorded since treatment started).

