9.3.7 Time to Next Treatment

The time to next treatment (TNT) is defined as the time from the date of enrollment to the institution of next treatment.

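### Scheduled follow-up stops at progression, before most time-to-next-treatment events; DOR omits death, TNT leaves death and censoring unstated, and DCR is listed under the wrong method

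*Combined protocol and SAP*

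**What the plan says.** Section 12.6 (Data Analysis Plans): "The analyses corresponding to secondary efficacy endpoints (PFS, DCR, DOR, TNT) will be summarized with typical" time-to-event analyses. The preceding paragraph, on the primary analysis, says: "We will calculate score-based confidence intervals for binomial proportions", with ORR and CRR as the worked cases.

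The definitions are in Section 9.3:

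- PFS (9.3.4): "A measurement from the date of enrollment until the criteria for disease progression (PD) is met or death occurs". Subjects without progression are censored at the last disease evaluation.
- DCR (9.3.5): "The disease control rate (DCR) is the proportion of all subjects with stable disease (SD) for 8 weeks, PR, or CR".
- DOR (9.3.6) runs from first CR or PR "until the date that recurrent or progressive disease is objectively documented".
- TNT (9.3.7) is "the time from the date of enrollment to the institution of next treatment".

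The cross-references add no rule. Section 12.2.2 points back to 9.3. Section 12.6.2 points to 12.3, which says only: "Additional secondary analyses include PFS, DCR, DOR, and TNT".

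On follow-up, Section 7.2 follows subjects until documented progression. Those who stop treatment without progression are contacted every 3 months for 1 year, by visit, phone or other means. Footnote 4 of the study calendar says the same, and disease progression is the only item under the calendar's follow-up heading.

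**The concern.** TNT is a stated secondary objective (2.1.2) and a listed endpoint (2.2.2). In this disease the next treatment usually starts after progression, so the schedule tends to stop before the event that TNT measures.

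Death adds to the problem. Section 1.3 says: "The median overall survival of relapsed/refractory PTCL in patients that are not candidates for high-dose therapy and autologous stem-cell transplantation is <6 months". That figure does not tell us what fraction die before a next treatment, but it makes such deaths plausible. If the plan does not say whether death ends TNT, censors it or competes with it, three analysts can report three different medians from the same data.

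For DOR, a responder who dies without documented progression has no stated endpoint, although the same death counts for PFS. If such deaths are censored, DOR reads longer than response ended by progression or death.

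DCR has no event time, so the method that 12.6 names for it does not fit its definition.

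**Working it through.** **1. The plan's own figures.** The only numbers in 12.6 are the score intervals. The 95% Wilson interval is [p + z²/2n ± z√(p(1−p)/n + z²/4n²)] / (1 + z²/n), with n = 33 and z = 1.96.

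- 17/33 gives 35.2% to 67.5%, and 7/33 gives 10.7% to 37.8%. Both match the plan.
- The same formula serves DCR. For assumed counts, 15/33 gives 29.8% to 62.0% and 20/33 gives 43.7% to 75.3%.

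**2. Definitions side by side.**

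| Endpoint | Ends at | Death | Censoring date |
|---|---|---|---|
| PFS (9.3.4) | progression or death | event | last disease evaluation |
| DOR (9.3.6) | documented recurrence or progression | not stated | not stated |
| TNT (9.3.7) | next treatment | not stated | not stated |
| DCR (9.3.5) | none; a proportion | not applicable | not applicable |

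**3. Routes by which next treatment or death could still be recorded.**

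- The eCRF takes the reason for stopping protocol therapy (6.3).
- AE and concomitant-medication contacts run to about 100 days after treatment (calendar, 7.1, 11.2.1).
- Section 14.2 provides for capturing selected standard-of-care data according to study objectives, and refers to DSOP guidelines that are not in the documents.
- SAE reports are a weak source of vital status, because death from progression is generally not reported as an SAE (11.1.2).

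**4. How far the unstated rule can move the TNT median (illustration only).** Let TNT = PFS + lag, both exponential, with full follow-up. Median PFS is 10 weeks, from the 23 CTCL/PTCL patients on nivolumab alone in Section 1.2. The lag and the share f who die before next treatment are assumptions. With one lag for deaths and treatment starts, S(t) = (b·e^(−at) − a·e^(−bt))/(b − a), where a = ln2/10 and b = ln2/lag.

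- Next treatment or death (composite): S = 0.5.
- Deaths censored: S^(1−f) = 0.5.
- Cumulative incidence of next treatment, death competing: (1−f)(1−S) = 0.5.

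For a lag of 6 weeks and f = 0.3, the required S values are 0.5, 0.5^(1/0.7) = 0.3715 and 1 − 0.5/0.7 = 0.2857. They are reached at 19.1, 24.4 and 28.8 weeks. Over a range (weeks, composite / censored / cumulative incidence):

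| Lag | f = 0.2 | f = 0.3 | f = 0.4 |
|---|---|---|---|
| 3 | 14.7 / 17.4 / 19.1 | 14.7 / 19.2 / 23.1 | 14.7 / 21.7 / 31.0 |
| 6 | 19.1 / 22.2 / 24.2 | 19.1 / 24.4 / 28.8 | 19.1 / 27.2 / 37.4 |
| 12 | 26.6 / 30.9 / 33.6 | 26.6 / 33.8 / 39.8 | 26.6 / 37.6 / 51.4 |

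With separate lags of 3 and 12 weeks for treatment and death, either way round (simulated), the deaths-censored median ranges from about 1.1 to 1.6 times the composite. If 10 to 30 points of a 30% death share are themselves PFS events and the lag is held at 6 weeks, the ratio is 1.30 to 1.37. At f = 0.5 the cumulative incidence never reaches 50%. The order of the three medians is the same throughout.

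**5. How much the 100-day contacts could reach (illustration only).** The share of treatment starts within 100 days of last dose is 1 − 2^(−w/lag), with w = (100 − gap)/7 weeks and gap the days from last dose to recorded progression. I took the gap from +14 to −56 days. It can be negative because Section 9.3 back-dates progression to the date of an earlier indeterminate response. Median lags of 3, 6 and 12 weeks give 94–99%, 76–92% and 51–72%. Falling inside the window does not mean that the date is recorded.

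**6. DOR.** Under constant hazards, censoring deaths multiplies the median by 1/(1−f). That is 1.05, 1.11 or 1.25 if 5%, 10% or 20% of responses end in death without documented progression (assumed shares).

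**The case against.** The strongest reply is that data collection is not visibly absent. Section 14.2 allows standard-of-care data to be captured according to study objectives; TNT is one, and a next treatment would often be standard of care. The eCRFs and DSOP guidelines may already hold the fields. This stands as a limit: the supportable claim is that no visible section schedules these items after progression. A reader might infer that TNT data will not be collected at all, and the documents do not support that.

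A reader might also infer that the TNT estimand is undefined. That goes too far. Section 9.3.7 gives both origin and event, and 'typical' time-to-event methods imply that event-free subjects are censored somewhere. What is missing is the handling of death and the censoring date.

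Nor is there a bias of known sign for TNT. Censoring deaths gives a longer median than the composite but a shorter one than cumulative incidence. A composite TNT is one acceptable choice, not a correction.

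Finally, the sizes rest on assumptions and the DCR point is unlikely to mislead an analyst. Both objections are fair, and the weight given to the point reflects them.

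**Conclusion.** The point holds as a minor-to-moderate one, confined to secondary endpoints. Its main substance is that visible scheduled follow-up ends before most TNT events would occur, so a stated objective risks being incompletely observed. Next come the omission of death from DOR, where the effect may be small, and the unstated TNT rule. DCR is a wording correction.

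The documents give no size. The spread of about 19, 24 or 29 weeks rests on a 10-week median PFS borrowed from another treatment setting and on an assumed 6-week lag and 30% death share; it shows that the choice matters, not what the trial would find. A reader should not carry the concern over to PFS, which has both a death event and a censoring rule, or to the two-stage decision on ORR and CRR.

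**What to change.** 1. **Section 7.2, the calendar and footnote 4.** Add next-treatment start date, vital status with date of death, and last-contact date. Collect them by the 3-monthly phone or clinic contact that 7.2 already permits, for 1 year after progression. If the DSOP guidelines or eCRFs already require this, cite them in 7.2 instead.
2. **Section 9.3.6.** End DOR at progression or death from any cause, whichever is first, censored at last disease evaluation as for PFS.
3. **Section 9.3.7.** State one rule before data are seen: for example, next treatment or death, or cumulative incidence of next treatment with death competing. Censor at last contact. Say whether study therapy resumed after observation in CR (Section 5) counts as next treatment.
4. **Section 12.6.** Remove DCR from the time-to-event list and report it as a proportion with the score interval.

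The cost is wording in these places, several eCRF fields, and up to 4 brief contacts per subject after progression: at most 4 × 33 = 132, fewer after deaths. DOR may read slightly shorter. Treatment, sample size and the decision rule do not change.
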